
Grade 1 No dose modification
 
Grade 2 Hold study drug/study regimen dose until Grade 2 resolution to Grade ≤ 1. If toxicity worsens, then treat as Grade 3 or Grade 4. Study drug/study regimen can be resumed once event stabilizes to Grade ≤ 1 after completion of steroid taper. Patients with endocrinopathies who may require prolonged or continued steroid replacement can be retreated with study drug/study regimen on the following conditions: 1. The event stabilizes and is controlled. 2. The patient is clinically stable as per Investigator or treating physician's clinical judgement. 3. Doses of prednisone are at ≤ 10 mg/day or equivalent.
	

Appendix 1

Dosing Modification and Toxicity Management Guidelines for Immune-Mediated, Infusion-Related, and Non-Immune-Mediated Reactions (MEDI4736 Monotherapy or Combination Therapy With Tremelimumab or Tremelimumab Monotherapy) - (1 November 2017 Version)

General Considerations

	Dose Modifications	Toxicity Management
Grade 3	Depending on the individual toxicity, study drug/study regimen may be permanently discontinued. Please refer to guidelines below.	immunosuppressive) should be considered for events not responding to systemic steroids. Progression to use of more potent immunosuppressives should proceed more rapidly in events with high likelihood for morbidity and/or mortality – e.g., myocarditis, or other similar events even if they are not currently noted in the guidelines – when these events are not responding to systemic steroids.

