Grade 4	Permanently discontinue study drug/study regimen. Note: For Grade ≥ 3 asymptomatic amylase or lipase levels, hold study drug/study regimen, and if complete work up shows no evidence of pancreatitis, study drug/study regimen may be continued or resumed. Note: Study drug/study regimen should be permanently discontinued in Grade 3 events with high likelihood for morbidity and/or mortality – e.g., myocarditis, or other similar events even if they are not currently noted in the guidelines. Similarly, consider whether study drug/study regimen should be permanently discontinued in Grade 2 events with high likelihood for morbidity and/or mortality – e.g., myocarditis, or other similar events even if they are not currently noted in the guidelines – when they do not rapidly improve to Grade <1 upon treatment with systemic steroids and following full taper Note: There are some exceptions to permanent discontinuation of study drug for Grade 4 events (i.e., hyperthyroidism, hypothyroidism, Type 1 diabetes mellitus).	
With long-term steroid and other immunosuppressive use, consider need for Pneumocystis jirovecii pneumonia (PJP, formerly known as Pneumocystis carinii pneumonia) prophylaxis, gastrointestinal protection, and glucose monitoring.Discontinuation of study drug/study regimen is not mandated for Grade 3/Grade 4 inflammatory reactions attributed to local tumor response (e.g., inflammatory reaction at sites of metastatic disease and lymph nodes). Continuation of study drug/study regimen in this situation should be based upon a benefit-risk analysis for that patient.

AE Adverse event; CTC Common Toxicity Criteria; CTCAE Common Terminology Criteria for Adverse Events; imAE immune-mediated adverse event; IV intravenous; NCI National Cancer Institute; PO By mouth.

Pediatric Considerations

Dose Modifications	Toxicity Management

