(e.g., hyperthyroidism, hypothyroidism, Type 1 diabetes mellitus, hypophysitis, hypopituitarism, and adrenal insufficiency; exocrine event of amylase/lipase increased also included in this section)	(depending on the type of endocrinopathy, refer to NCI CTCAE v4.03 for defining the CTC grade/severity)		
– Consider consulting an endocrinologist for endocrine events.– Consider, as necessary, discussing with study physician.– Monitor patients for signs and symptoms of endocrinopathies. Non-specific symptoms include headache, fatigue, behavior changes, changed mental status, vertigo, abdominal pain, unusual bowel habits, polydipsia, polyuria, hypotension, and weakness.– Patients should be thoroughly evaluated to rule out any alternative etiology (e.g., disease progression including brain metastases, or infections).– Depending on the suspected endocrinopathy, monitor and evaluate thyroid function tests: TSH, free T3 and free T4 and other relevant endocrine and related labs (e.g., blood glucose and ketone levels, HgA1c).– For modest asymptomatic elevations in serum amylase and lipase, corticosteroid treatment is not indicated as long as there are no other signs or symptoms of pancreatic inflammation.– If a patient experiences an AE that is thought to be possibly of autoimmune nature (e.g., thyroiditis, pancreatitis, hypophysitis, or diabetes insipidus), the investigator should send a blood sample for appropriate autoimmune antibody testing.

Grade 1

No dose modifications.

Grade 2

For Grade 2 endocrinopathy other than hypothyroidism and Type 1 diabetes mellitus, hold study drug/study regimen dose until patient is clinically stable.

- If toxicity worsens, then treat as Grade 3 or Grade 4.

Study drug/study regimen can be resumed once event stabilizes and after completion of steroid taper.

Patients with endocrinopathies who may require prolonged or continued steroid replacement (e.g., adrenal insufficiency) can be retreated with study drug/study regimen on the following conditions:

1. The event stabilizes and is controlled.
2. The patient is clinically stable as per investigator or treating physician's clinical judgement.
3. Doses of prednisone are ≤ 10 mg/day or equivalent.

Grade 3 or 4

For Grade 3 or 4 endocrinopathy other than hypothyroidism and Type 1 diabetes

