
mellitus, hold study drug/study regimen dose until endocrinopathy symptom(s) are controlled.
 
Study drug/study regimen can be resumed once event stabilizes and after completion of steroid taper.
 
Patients with endocrinopathies who may require prolonged or continued steroid replacement (e.g., adrenal insufficiency) can be retreated with study drug/study regimen on the following conditions:
 
 1. The event stabilizes and is controlled. 2. The patient is clinically stable as per investigator or treating physician's clinical judgement. 3. Doses of prednisone are ≤ 10 mg/day or equivalent. 	
function and, as indicated by suspected endocrinopathy and as clinically indicated, consider pituitary scan. Hospitalization recommended.
 
 – For all patients with abnormal endocrine work up, except those with isolated hypothyroidism or Type 1 DM, and as guided by an endocrinologist, promptly initiate empiric IV methylprednisolone 1 to 2 mg/kg/day or equivalent, as well as relevant hormone replacement (e.g., hydrocortisone, sex hormones). – For adrenal crisis, severe dehydration, hypotension, or shock, immediately initiate IV corticosteroids with mineralocorticoid activity. – Isolated hypothyroidism may be treated with replacement therapy, without study drug/study regimen interruption, and without corticosteroids. – Isolated Type 1 diabetes mellitus may be treated with appropriate diabetic therapy, without study drug/study regimen interruption, and without corticosteroids. – Once patients on steroids are improving, gradually taper immunosuppressive steroids (as appropriate and with guidance of endocrinologist) over ≥ 28 days and consider prophylactic antibiotics, antifungals, and anti-PJP treatment (refer to current NCCN guidelines for treatment of cancer-related infections [Category 2B recommendation]).^a
---	--

Neurotoxicity	Any Grade	General Guidance	For Any Grade:

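### Appendix 1 contradicts itself on whether study drug may be resumed after Grade 4 hypophysitis, hypopituitarism or adrenal insufficiency

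*Combined protocol and SAP*

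**What the plan says.** Appendix 1 opens with a General Considerations table organised by grade, followed by a table of specific immune-mediated reactions organised by organ system.

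The general Grade 4 cell begins: "Permanently discontinue study drug/study regimen. Note: For Grade ≥ 3 asymptomatic amylase or lipase levels, hold study drug/study regimen". It ends with a note on exceptions: "There are some exceptions to permanent discontinuation of study drug for Grade 4 events (i.e., hyperthyroidism, hypothyroidism, Type 1 diabetes mellitus". The neighbouring toxicity-management column adds that discontinuation is not mandatory for Grade 3 or 4 inflammation attributed to local tumor response.

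The general Grade 3 cell is worded differently and sends the reader onward: "Depending on the individual toxicity, study drug/study regimen may be permanently discontinued. Please refer to guidelines below".

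In the specific table, the endocrinopathy row gives its scope as "hyperthyroidism, hypothyroidism, Type 1 diabetes mellitus, hypophysitis, hypopituitarism, and adrenal insufficiency", together with raised amylase or lipase. Its cell for the two highest grades starts "For Grade 3 or 4 endocrinopathy other than hypothyroidism and Type 1 diabetes" mellitus and instructs the investigator to "hold study drug/study regimen dose until endocrinopathy symptom(s) are controlled". It continues: "Study drug/study regimen can be resumed once event stabilizes and after completion of steroid taper". Patients who need prolonged or continued "steroid replacement (e.g., adrenal insufficiency) can be retreated with study drug/study regimen on the following conditions": a controlled event, clinical stability, and prednisone at or below 10 mg/day or equivalent.

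Section 13.1 stops investigational product for any adverse event that meets the discontinuation criteria of section 11. Section 11.1 (schedule modification and toxicity management) refers to Appendix 1 for the detail.

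**The concern.** The two cells overlap for a definable set of patients: those with a Grade 4 endocrine event that the row covers but the general exception note does not name. For them, one cell ends treatment and the other leaves resumption open.

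These events are foreseeable. Section 11.3 lists hypophysitis/hypopituitarism and adrenal insufficiency among the adverse events of special interest already observed with these drugs. Two investigators could each follow Appendix 1 and reach different decisions on further exposure after a life-threatening event, and a monitor would have no text for deciding whether either had deviated. The choice also settles whether section 13.1 applies and whether the patient moves to the Appendix 2 follow-up schedule.

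**Working it through.** No arithmetic applies. The check compares the two cells for each named endocrine event at Grade 4, then looks for any rule that ranks them.

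**Step 1: the cells side by side at Grade 4.**

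| Event | General Grade 4 cell | Endocrinopathy Grade 3 or 4 cell | Agree? |
|---|---|---|---|
| Hypothyroidism | Listed exception | Outside the hold rule | Yes |
| Type 1 diabetes mellitus | Listed exception | Outside the hold rule | Yes |
| Hyperthyroidism | Listed exception | Hold, may resume | Yes |
| Hypophysitis | Discontinue permanently | Hold, may resume | No |
| Hypopituitarism | Discontinue permanently | Hold, may resume | No |
| Adrenal insufficiency | Discontinue permanently | Hold, may resume (named example for retreatment on steroid replacement) | No |

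The conflict is confined to three events at Grade 4. At Grade 3 there is none, because the general cell defers to the specific rows.

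**Step 2: do the other allowances in the general table help?** There are two: asymptomatic amylase or lipase elevation, and inflammation attributed to local tumor response. Neither describes the three events.

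**Step 3: is there a precedence rule?** None was found in Appendix 1, section 11 or section 13.1. The one explicit deferral to the specific guidelines is in the general Grade 3 cell. The Grade 4 cell has no such sentence and gives its own exceptions, introduced by i.e. Those exceptions are all endocrine, so they would be unnecessary if the endocrinopathy row simply overrode the general cell. The general Grade 2 cell repeats the allowance for patients on steroid replacement; the general Grade 4 cell does not.

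**Step 4: can the answer be read from the other organ rows?** No. The pneumonitis, colitis, hepatitis, nephritis, rash, neurotoxicity, peripheral neuromotor, myocarditis and myositis rows all discontinue permanently at Grade 4. The endocrinopathy row is the only one in that table that does not.

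**Step 5: what does resuming mean?** Under sections 4.3 and 9.1, tremelimumab is given with durvalumab for up to 4 cycles, followed by up to 9 cycles of durvalumab alone (4 + 9 = 13). Resumption therefore involves both agents during cycles 1-4 and durvalumab alone in cycles 5-13.

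**The case against.** The strongest reply is that the specific table governs. The first table is labelled general and the organ table specific, and the endocrinopathy row plainly had severe events in view, since its management column deals with adrenal crisis and shock. The exception note speaks only of some exceptions, and the table holds two allowances outside that note, so it is not a rule with exactly three exceptions. This is a reasonable reading, but it is inferred from layout. The documents do not state it, and the general Grade 3 cell shows that the appendix says so when it means to defer.

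A second reply is that the guidance leaves room for judgment. Section 11.1 says it may be applied, and section 11.3 describes the guidelines as helping the investigator exercise clinical judgment. Resumption in the endocrinopathy row is permissive and conditional, so an investigator who stops for good breaches neither cell. That stands. A reader might infer that the two cells command opposite actions; they do not. They differ on whether the patient is eligible to resume.

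A reader might also infer that resumption always means re-exposure to the combination. It does not after cycle 4 of a treatment course.

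Finally, a reader might infer that the safety results become irreproducible. The documents do not support that. Section 14.3 tabulates adverse events, so the index event is counted under either instruction, and only events after resumption could differ. No discontinuation-for-toxicity endpoint is defined. Section 14.2 keeps patients who stop for toxicity in response follow-up. Appendix 2 scans them every 8 weeks for the first 48 weeks, the same interval as on treatment (every 2 cycles of 4 weeks, 2 × 4 = 8).

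**Conclusion.** Wrong as written: this is an internal contradiction, not a design choice. For Grade 4 hypophysitis, hypopituitarism and adrenal insufficiency, eligibility to resume study drug, and removal from treatment under section 13.1, depend on which Appendix 1 cell is read.

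The reach is narrow: three events, one grade. It is tempting to attach a probability that at least one of the 27 patients is affected, but the documents give no rate for these events. The phase Ib combination results summarised in section 3.4.3 name diarrhea, colitis and raised lipase as the most frequent Grade 3-4 events and give no endocrine figure. A rate for all Grade 4 endocrinopathy would also include events on which the two cells agree.

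The two-stage design (13 + 14 = 27 patients, 4 or more responses) is unaffected, and any effect on the safety tabulation is indirect, through later exposure. The point matters because it concerns further dosing after a life-threatening event. The conclusion assumes only that the exception note means what i.e. ordinarily means and that no precedence rule exists elsewhere in the documents. It takes no position on which instruction is clinically right.

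**What to change.** Reconcile the general Grade 4 cell with the endocrinopathy Grade 3 or 4 cell for hypophysitis, hypopituitarism and adrenal insufficiency. This can be done by aligning the general exception list with the row, or by giving the row a separate Grade 4 instruction that matches the general cell. The sponsor's clinicians decide which rule applies.

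Add one sentence stating which table governs if the general and specific tables differ. It can go in Appendix 1 or, if that dated guideline text is not to be edited, in section 11.1.

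The cost is an amendment to wording. Sample size, assessments and analysis do not change.

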
Drug administration modifications of study drug/study regimen will be made to manage potential immune-related AEs based on severity of treatment-emergent toxicities graded per NCI CTCAE v4.03.
 
In addition to the criteria for permanent discontinuation of study drug/study regimen based on CTC grade/severity (table below), permanently discontinue study drug/study regimen for the following conditions:
 
• Inability to reduce corticosteroid to a dose of ≤ 10 mg of prednisone per day (or equivalent) within 12 weeks after last dose of study drug/study regimen• Recurrence of a previously experienced Grade 3 treatment-related AE following resumption of dosing	
It is recommended that management of immune-mediated adverse events (imAEs) follows the guidelines presented in this table:
 
– It is possible that events with an inflammatory or immune mediated mechanism could occur in nearly all organs, some of them not noted specifically in these guidelines.– Whether specific immune-mediated events (and/or laboratory indicators of such events) are noted in these guidelines or not, patients should be thoroughly evaluated to rule out any alternative etiology (e.g., disease progression, concomitant medications, and infections) to a possible immune-mediated event. In the absence of a clear alternative etiology, all such events should be managed as if they were immune related. General recommendations follow.– Symptomatic and topical therapy should be considered for low-grade (Grade 1 or 2, unless otherwise specified) events.– For persistent (>3 to 5 days) low-grade (Grade 2) or severe (Grade ≥ 3) events, promptly start prednisone 1 to 2 mg/kg/day PO or IV equivalent.– Some events with high likelihood for morbidity and/or mortality – e.g., myocarditis, or other similar events even if they are not currently noted in the guidelines – should progress rapidly to high dose IV corticosteroids (methylprednisolone at 2 to 4 mg/kg/day) even if the event is Grade 2, and if clinical suspicion is high and/or there has been clinical confirmation. Consider, as necessary, discussing with the study physician, and promptly pursue specialist consultation.– If symptoms recur or worsen during corticosteroid tapering (28 days of taper), increase the corticosteroid dose (prednisone dose [e.g., up to 2 to 4 mg/kg/day PO or IV equivalent]) until stabilization or improvement of symptoms, then resume corticosteroid tapering at a slower rate (>28 days of taper).– More potent immunosuppressives such as TNF inhibitors (e.g., infliximab) (also refer to the individual sections of the imAEs for specific type of

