- Manage dosing for Grade 2 transaminase rise as instructed for Grade 3 transaminase rise
- Grade 3-4: Permanently discontinue study drug/study regimen

Nephritis or renal dysfunction (elevated serum creatinine)	Any Grade	General Guidance	For Any Grade: 
- Consult with nephrologist.- Monitor for signs and symptoms that may be related to changes in renal function (e.g., routine urinalysis, elevated serum BUN and creatinine, decreased creatinine clearance, electrolyte imbalance, decrease in urine output, or proteinuria).- Patients should be thoroughly evaluated to rule out any alternative etiology (e.g., disease progression or infections).- Steroids should be considered in the absence of clear alternative etiology even for low-grade events (Grade 2), in order to prevent potential progression to higher grade event.
Grade 1 (Serum creatinine > 1	No dose modifications.		For Grade 1: 
- Monitor serum creatinine weekly and any accompanying

to $1.5 \times$ baseline; >
ULN to $1.5 \times$ ULN)

symptoms.

- If creatinine returns to baseline, resume its regular monitoring per study protocol.
- If creatinine worsens, depending on the severity, treat as Grade 2, 3, or 4.
- Consider symptomatic treatment, including hydration, electrolyte replacement, and diuretics.

Grade 2
(serum creatinine >1.5
to $3.0 \times$ baseline; >1.5
to $3.0 \times$ ULN)

Hold study drug/study regimen until resolution to Grade ≤ 1 or baseline.

- If toxicity worsens, then treat as Grade 3 or 4.
- If toxicity improves to Grade ≤ 1 or baseline, then resume study drug/study regimen after completion of steroid taper.

For Grade 2:

- Consider symptomatic treatment, including hydration, electrolyte replacement, and diuretics.
- Carefully monitor serum creatinine every 2 to 3 days and as clinically warranted.
- Consult nephrologist and consider renal biopsy if clinically indicated.
- If event is persistent (>3 to 5 days) or worsens, promptly start prednisone 1 to 2 mg/kg/day PO or IV equivalent.
- If event is not responsive within 3 to 5 days or worsens despite prednisone at 1 to 2 mg/kg/day PO or IV equivalent, additional workup should be considered and prompt treatment with IV methylprednisolone at 2 to 4 mg/kg/day started.

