- Once the patient is improving, gradually taper steroids over ≥ 28 days and consider prophylactic antibiotics, antifungals, and anti-PJP treatment (refer to current NCCN guidelines for treatment of cancer-related infections [Category 2B recommendation]).^a
- When event returns to baseline, resume study drug/study regimen and routine serum creatinine monitoring per study protocol.

Grade 3 or 4
(Grade 3: serum
creatinine
 $>3.0 \times$ baseline; >3.0 to
 $6.0 \times$ ULN;

Grade 4: serum
creatinine $>6.0 \times$ ULN)

Permanently discontinue study drug/study regimen.

For Grade 3 or 4:

- Carefully monitor serum creatinine on daily basis.
- Consult nephrologist and consider renal biopsy if clinically indicated.
- Promptly start prednisone 1 to 2 mg/kg/day PO or IV equivalent.
- If event is not responsive within 3 to 5 days or worsens despite prednisone at 1 to 2 mg/kg/day PO or IV equivalent, additional workup should be considered and prompt treatment with IV methylprednisolone 2 to 4 mg/kg/day started.

- Once the patient is improving, gradually taper steroids over ≥ 28 days and consider prophylactic antibiotics, antifungals, and anti-PJP treatment (refer to current NCCN guidelines for treatment of cancer-related infections [Category 2B recommendation]).^a

Rash	Any Grade	General Guidance	For Any Grade:
(excluding bullous skin formations)	(refer to NCI CTCAE v 4.03 for definition of severity/grade depending on type of skin rash)		
 Monitor for signs and symptoms of dermatitis (rash and pruritus). IF THERE IS ANY BULLOUS FORMATION, THE STUDY PHYSICIAN SHOULD BE CONTACTED AND STUDY DRUG DISCONTINUED.
Grade 1	No dose modifications.		For Grade 1: 
 Consider symptomatic treatment, including oral antipruritics (e.g., diphenhydramine or hydroxyzine) and topical therapy (e.g., urea cream).

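### Appendix 1, Grade 2 nephritis: one bullet restarts study drug at return to baseline, which disagrees with the same row's dosing rule on both the steroid taper and the recovery threshold

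*Combined protocol and SAP*

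**What the plan says.** Appendix 1 sets out each immune-mediated reaction with a Dose Modifications cell and a Toxicity Management cell side by side. For nephritis or renal dysfunction at Grade 2:

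- **Dose Modifications.** Study drug is held. If toxicity falls to Grade 1 or below "or baseline, then resume study drug/study regimen after completion of steroid taper".
- **Toxicity Management, steroids.** Prednisone starts if the event persists beyond 3 to 5 days or worsens. The next-to-last bullet begins "Once the patient is improving, gradually taper steroids over" and sets a minimum of 28 days.
- **Toxicity Management, last bullet.** "When event returns to baseline, resume study drug/study regimen and routine serum creatinine monitoring per study protocol".

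Two neighbouring texts bear on this row. The general Grade 2 rule at the head of Appendix 1 allows restart at Grade 1 or below "after completion of steroid taper. Patients with endocrinopathies who may require prolonged or continued steroid replacement can be retreated" under listed conditions. The Grade 1 nephritis row says "If creatinine returns to baseline, resume its regular monitoring per study protocol", which concerns monitoring only.

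Section 11.1 (Schedule modification and toxicity management) sends the investigator to Appendix 1 for these decisions, so the table is in operational use.

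**The concern.** One row answers the question of when to re-dose in two ways. The dosing cell asks for recovery and a finished taper. The last bullet asks only for return to baseline. A patient improving on prednisone can reach baseline creatinine while still tapering; the bullet then says restart and the dosing cell says wait.

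What is at stake is a checkpoint-inhibitor dose given while an immune-mediated renal event is still being treated. Appendix 1 itself foresees symptoms recurring or worsening during a taper and responds by raising the steroid dose. Nephritis is a listed event of special interest (section 11.3), and eligibility admits patients with creatinine clearance just above 30 mL/min (section 6.2).

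The two instructions also use different recovery thresholds, so a repair aimed only at the taper would leave part of the disagreement in place.

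**Working it through.** The plan states no figure to reproduce here. The check is a comparison of the texts, followed by a simple count of days.

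**Step 1. The two rules by patient state.** In this row Grade 1 means creatinine above 1 and up to 1.5 times baseline, or above the upper limit of normal and up to 1.5 times that limit, so Grade 1 and baseline are different states.

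| State | Last bullet | Dosing cell |
|---|---|---|
| Baseline, taper still running | restart | wait |
| Baseline, taper finished | restart | restart |
| Grade 1 above baseline, taper finished | not yet triggered | restart |
| Grade 1 above baseline, taper still running | not yet triggered | wait |
| Baseline, never on steroids | restart | restart |
| Grade 1 above baseline, never on steroids | not yet triggered | restart |

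The first line is the safety conflict. The third and sixth lines are the threshold mismatch, where the bullet is the stricter of the two.

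**Step 2. Does another rule block the early dose?** The general Grade 2 rule sides with the dosing cell, and its allowance for continued steroid replacement covers endocrinopathies only. The concomitant-treatment rule in section 9.3 does not help, because it exempts steroids given for drug-related events. The taper condition is therefore the safeguard, and it is the one the bullet leaves out.

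**Step 3. Size of the gap.** Inputs: minimum taper T = 28 days (Appendix 1) and cycle length 28 days (section 10.0). Let b be the taper day on which creatinine reaches baseline.

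Gap between the two restart dates = T − b.

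| b (days) | 0 | 7 | 14 | 21 | 28 |
|---|---|---|---|---|---|
| Gap (days) | 28 | 21 | 14 | 7 | 0 |

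The largest gap at T = 28 is 28/28 = 1 cycle, or about one dose per episode. A longer taper widens it. The values of b are illustrative, since the documents do not say when baseline is usually reached.

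**Step 4. Is waiting feasible?** Section 11.1 allows suspension for up to 12 weeks (84 days) beyond the scheduled infusion date. A minimum taper uses 28 of those days and leaves 84 − 28 = 56 for time before the taper or for a longer one.

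**The case against.** The strongest reply is that the right rule is already on the page twice, in the adjacent cell and in the general Grade 2 rule, and that an investigator deciding on re-dosing looks in the dosing column. Appendix 1 supports this by its tone. For dosing, "Drug administration modifications of study drug/study regimen will be made to manage potential immune-related AEs"; for management, "It is recommended that management of immune-mediated adverse events (imAEs) follows the guidelines presented in this table". Section 11.3 adds that the guidelines exist to assist clinical judgment. The bullet omits the taper condition without contradicting it in words, it follows directly after the taper bullet, and its closing reference to the study protocol might be read as covering the restart too. The Grade 2 dosing cells for peripheral neuromotor syndromes and for myositis are also silent on the taper, and there the general rule is taken to fill the gap.

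Most of this stands, and it is why the point is minor. It does not dispose of it. Appendix 1 states no precedence between columns. The Toxicity Management column carries binding drug instructions elsewhere: for bullous skin formation, "THE STUDY PHYSICIAN SHOULD BE CONTACTED AND STUDY DRUG DISCONTINUED". That instruction conflicts with no dosing cell, so it does not show this column overriding the other, but it does show that a reader may expect to find drug decisions there. Reading the last two bullets as a sequence is possible, yet the trigger actually stated is return to baseline. Where a text is merely silent, the general rule can fill in; here the bullet states its own trigger for restart.

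A reader might infer that the plan deliberately allows re-dosing on steroids after nephritis. The documents do not support that: two current rules forbid it, and the Grade 1 bullet, which returns only to monitoring, suggests a drafting slip. Nor is this the only Grade 2 text in Appendix 1 that omits the taper.

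**Conclusion.** The bullet is wrong as written. It departs from the governing rule on the taper, where it is looser, and on the recovery threshold, where it is stricter. This is an internal inconsistency of minor safety weight and should be corrected at the next amendment.

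Under the minimum taper, the worst case is a restart 28 days early, or about one dose per episode. That requires steroids to have been started, baseline to be reached before the taper ends, a dose to fall due in that window, and the investigator to follow the bullet over the cell beside it. The documents give no frequency for any of these, so no expected number of early doses is claimed.

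A reader might go further and see a threat to the trial's results or evidence of likely renal harm. Neither follows. The response endpoint, the sample of 27 and the two-stage decision rule do not depend on this text, and nothing in the documents quantifies harm from a dose given during a taper.

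**What to change.** Either of two changes settles both mismatches.

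1. Confine the bullet to monitoring, as the Grade 1 row does, for example: *Once creatinine is back to baseline, return to the protocol's routine creatinine schedule.* Restart is then decided by the dosing cell alone.
2. Leave Appendix 1 as it is and add one line to section 11.1: *The Dose Modifications column of Appendix 1 governs resumption of study drug; where a Grade 2 immune-mediated row is silent on the steroid taper, the general Grade 2 rule applies.* This also covers the neuromotor and myositis rows.

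Adding only a taper condition to the bullet is not enough: it would still require baseline where the dosing cell accepts Grade 1.

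The cost is one sentence, with no added patients, visits or tests. The first option makes this trial's copy differ from the guideline version dated 1 November 2017; the second avoids that and is preferable if the guideline text is to stay intact.
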